#### Section D: Purpose and Objectives

- Aim 1: To determine the feasibility and reliability of skin carotenoid measurement in infants.
- Aim 2: To determine the mean carotenoid intakes and mean plasma carotenoid concentrations in infants.
- Aim 3: To assess the validity of skin carotenoid scores as a correlate of plasma carotenoid concentrations and carotenoid intake in infants.
- Aim 4. To determine the relative validity of different infant dietary assessment tools for estimating infant carotenoid intake, energy intake, and food group intake at 4, 6, and 8 months of age.

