Dietary Assessment: At each study visit, usual infant consumption of breast milk and/or formula intake (including brand), fruits and vegetables, and other carotenoid-rich foods (e.g. eggs) will be assessed by 7 day recall using a validated infant food frequency questionnaire (FFQ) (2). This FFQ is analyzed using Nutrient Data System for Research (Univ Minnesota) software by the MRU registered dietician ([name], RD) and yields food group and nutrient intake data including carotenoids. Dietary intake will be assessed during the 1 week prior to the 6- and 8-month-old study visits through 3x24 hour dietary recalls (2 weekdays and 1 weekend day) using ASA24 (NIH/NCI), a confidential, online tool. In order to assist caregivers in remembering and finding out about what their infant ate each day, they will be given an Infant Food Diary in which to record everything their infant ate during the queried 7 day period. The Food Diaries will be collected at visits 2 & 3 for our records. Research staff will follow-up with the subjects by phone to clarify any food responses as needed. These 24 hour recalls will be analyzed for energy intake, fruit and vegetable servings, and carotenoid intake. If the participants cannot access the ASA24 food survey using their device, the research staff will call them by phone and ask the ASA24 questions in order to complete the recall.

Dermal Carotenoid Assessment: Pressure-mediated RS ("Veggie Meter") will measure dermal carotenoid intensity. Before use, the device is calibrated. The same index finger of the infant is cleaned with an alcohol wipe and placed on the device's lens for 10 s at each visit. Triplicate readings are recorded electronically. Because some infants' fingers may be too small to obtain a reproducible reading, we will also collect a back-up measurement of the infant's heel using the same procedure as for the finger. This device will not diagnose or treat a disease or condition, so will not require FDA Investigational Device Exemption.

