## Section G: Sample Size/Data Analysis

### G1. Sample Size

How many subjects (or specimens, or charts) will be used in this study?

Local: 21 Worldwide: 21

Please indicate why you chose the sample size proposed:

A final n=21 is sufficient to estimate the mean time required to measure skin carotenoid concentrations in 4 month olds, to estimate the reliability of skin carotenoid score measurements in 4 month olds, obtain estimates for mean and SD skin carotenoid scores in 4 month olds, and examine the correlation between skin carotenoid scores and plasma carotenoid concentrations and carotenoid intake in 4 month olds.

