## G2. Data Analysis

Provide a description of your plan for data analysis. State the types of comparisons you plan (e.g. comparison of means, comparison of proportions, regressions, analysis of variance). Which is the PRIMARY comparison/analysis? How will the analyses proposed relate to the primary purposes of your study?

Experimental Question 1: Assess the feasibility of triplicate skin carotenoid measurements in infants by calculating the mean time required for measurement.

Approach - mean time to measure skin carotenoid scores in triplicate at the finger and heel were calculated in 4, 6, and 8 month olds (primary endpoint is 4 month old measurements).

Experimental Question 2: The effect of replicate measurements (3 versus up to 6 replicates) on measurement reliability in 4, 6, and 8 month olds.

Approach: Calculate the intraclass correlation coefficients and 95% confidence intervals using generalized linear mixed models with restricted maximum likelihood. Models specify a random replicate effect with nesting of replicates within infant and no covariates. ICC is calculated by dividing the variance effect for replicate by the total variance.

Experimental Question 3: Calculate the mean skin carotenoid scores, plasma carotenoid concentrations, and carotenoid intakes in infants.

Approach: Mean and standard deviation skin carotenoid scores, plasma carotenoid concentrations, and carotenoid intakes are calculated for 4, 6, and 8 month old infants.

Exploratory Questions: The correlation between skin carotenoid scores, at the finger or heel, with dietary carotenoid intake and total plasma carotenoid concentrations in 4, 6, and 8 month olds.

Approach: Generalized linear mixed models controlled for age, skin measurement location, and their interaction, with either plasma carotenoids or dietary carotenoid intake as predictors of the outcome skin carotenoid scores.

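### The planned ICC cannot show what 3 versus up to 6 readings do to reliability, its numerator is ambiguous, and the procedure describes only triplicates

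*Combined protocol and SAP*

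**What the plan says.** Section G2, Experimental Question 2, sets the question: "The effect of replicate measurements (3 versus up to 6 replicates) on measurement reliability in 4, 6, and 8 month olds". Section C lists the effect of replication on reliability among the matters to settle before controlled feeding studies.

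The approach is an ICC with a 95% confidence interval from mixed models fitted by restricted maximum likelihood. The model is described thus: "Models specify a random replicate effect with nesting of replicates within infant and no covariates". The ratio is described thus: "ICC is calculated by dividing the variance effect for replicate by the total variance". G2 gives no formula for the reliability of an averaged score and no rule for comparing results from 3 and from 6 readings.

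On the number of readings, section F2 (Dermal Carotenoid Assessment) says of the finger: "Triplicate readings are recorded electronically". It adds a back-up heel measurement "using the same procedure as for the finger". Experimental Question 1 agrees, planning the "mean time to measure skin carotenoid scores in triplicate at the finger and heel".

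Reliability is part of Aim 1 in section D ("To determine the feasibility and reliability of skin carotenoid measurement in infants") and one of the reasons given in G1 for 21 infants ("to estimate the reliability of skin carotenoid score measurements in 4 month olds").

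**The concern.** There are three linked problems.

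1. **The statistic does not match the question.** A variance component divided by total variance contains no term for the number of readings averaged. If the readings are exchangeable, the 3-reading and 6-reading analyses estimate the same number. A reader would probably conclude that extra readings add nothing, although averaging more readings does make the score more reliable.

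2. **The numerator is ambiguous.** With replicates nested within infant, the variance attributed to replicate can be read as the within-infant term. The ratio is then 1 minus the usual ICC and falls as reliability improves.

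3. **Readings 4 to 6 have no source.** F2 and Question 1 give three readings per site. Nothing says when, in whom or at which site more are taken. If the six are three finger plus three heel readings, they are not six replicates of one measurement, and the reliability model has no site term.

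The first problem affects the answer to Question 2. The second affects any reliability figure reported under Aim 1.

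**Working it through.** **Inputs.** The documents give n = 21 (G1), 3 versus up to 6 readings (G2) and the ICC definition (G2). They give no ICC, target or interval width, so there is no figure of the plan's to reproduce. I assume single-reading ICCs of 0.50 to 0.95.

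**Step 1: what depends on k.** Let Vb be the between-infant and Vw the within-infant variance.

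- Single reading: ICC = Vb/(Vb + Vw). There is no k in it.
- Mean of k readings: R(k) = Vb/(Vb + Vw/k) = k*ICC/(1 + (k-1)*ICC).

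At ICC 0.80, R(3) = 2.40/2.60 = 0.923 and R(6) = 4.80/5.00 = 0.960.

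| Assumed ICC | R(3) | R(6) | Gain |
|---|---|---|---|
| 0.50 | 0.750 | 0.857 | 0.107 |
| 0.60 | 0.818 | 0.900 | 0.082 |
| 0.80 | 0.923 | 0.960 | 0.037 |
| 0.95 | 0.983 | 0.991 | 0.009 |

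(The last gain is taken before rounding.)

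**Step 2: what the planned ICC would show.** I simulated a balanced one-way random-effects model with 21 infants and 20,000 runs per setting. The ICC came from the first 3 and from all 6 readings of the same infants, with exact F-based intervals.

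| Assumed ICC | Mean estimate, 3 readings | Mean estimate, 6 readings |
|---|---|---|
| 0.60 | 0.582 | 0.584 |
| 0.80 | 0.785 | 0.786 |

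At 0.80 the median 95% interval narrows from 0.636–0.904 to 0.671–0.896, and the 6-reading ICC is the lower of the two in 50% of runs. Repeat runs differ only in the third decimal.

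**Step 3: the numerator.** With Vw on top, the ratio is Vw/(Vb + Vw) = 1 - ICC. Where the usual estimates average 0.785 and 0.786, the plan would report 0.215 and 0.214.

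**Step 4: if the six readings are three finger plus three heel.** Suppose ICC 0.80 at each site, a finger-heel true-score correlation c and no mean shift. Of the 15 pairs among six readings, 6 are within a site (covariance 0.80) and 9 are across sites (covariance 0.80c). A model without a site term targets their average. For c = 0.8 that is (6*0.80 + 9*0.64)/15 = 0.704, and the simulated estimate averages 0.687, against 0.785 for one site. Over c = 0.6 to 1.0 the estimate averages 0.594 to 0.785.

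**Step 5: whether triplicates suffice.** R(k) rises steadily with the ICC, so ICC limits convert directly. At ICC 0.80 the triplicate limits 0.636 and 0.904 become:

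- k = 3: 1.908/2.272 = 0.840 and 2.712/2.808 = 0.966
- k = 6: 3.816/4.180 = 0.913 and 5.424/5.520 = 0.983

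**Step 6: sensitivity to exchangeability.** Let readings 4 to 6 have twice the within-infant variance (0.40 instead of 0.20). The error variance of the six-reading mean is (3*0.20 + 3*0.40)/36 = 0.05, so true reliability is 0.80/0.85 = 0.941, where the formula gives 0.960. The planned ICC averages 0.785 from the first three readings and 0.711 from all six. It falls although the averaged score is still more reliable than at k = 3 (0.923).

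**The case against.** - **Scope.** Aim 1 and the sample-size statement ask for reliability in general, not for a 3-versus-6 contrast. A correctly defined single-reading ICC would serve both. This stands: the mismatch in the statistic affects only Question 2 and its counterpart in section C. The numerator problem does reach Aim 1.
- **Exchangeability.** Later readings in infants may be noisier, and comparing ICCs could reveal that. It is a legitimate use, and the fix keeps it as a descriptive check. It does not measure the gain from averaging, and step 6 shows that the two can move in opposite directions.
- **Numerator.** The plan calls the quantity an intraclass correlation, so the infant-level variance was probably intended. That is plausible, and 0.215 is what the unfavourable reading would give, not an expected result. The text still allows it.
- **Pooled sites.** No section says finger and heel readings are pooled, and having no covariates is compatible with separate models by site. Step 4 is therefore hypothetical. It matters because three plus three is the only route to six that F2 offers.
- **Simulation.** Six readings in every infant and exact F intervals are simpler than a variable count and mixed-model intervals, so the interval widths are illustrative. The absence of k from the ICC does not depend on the simulation.
- **Size.** At a very high ICC the gain is slight, 0.009 at 0.95. That is correct, but the plan cannot know beforehand that it is in that range.

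**Conclusion.** The concern holds and should be fixed. As written, the 3-versus-6 comparison is expected to show no difference except interval width, whereas the reliability of the averaged score rises by 0.107 at an assumed ICC of 0.50, by 0.037 at 0.80 and by 0.009 at 0.95. These figures rest on assumed ICCs and exchangeable readings. The missing k, the ambiguous numerator and the conflict over the number of readings rest on the text alone, and nothing elsewhere in the documents resolves them. The flaw is not fatal: no data are lost, and once the numerator is settled the ICC converts to the needed quantity in closed form.

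**What to change.** 1. Reconcile F2 and G2 on the number of readings per site and visit. If more than three are taken, say when, in whom and at which site.
2. State that the ICC numerator is the between-infant variance.
3. Estimate the variance components separately for finger and heel and for each age.
4. For k = 1 to 6, report k*ICC/(1 + (k-1)*ICC) with 95% limits obtained by transforming the ICC limits. State the assumption that later readings behave like earlier ones.
5. Where readings 4 to 6 exist, compare the variance components from the first three and from all readings in the same infants, as a descriptive check.

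**Cost.** Analysis wording and one clarified sentence in F2, with no extra readings, infants or visits. If only triplicates exist, results for k = 4 to 6 are extrapolations under the stated assumption. The check in item 5 is weak with 21 infants: by chance alone the paired difference in ICC has an SD of 0.037 at an ICC of 0.80 (0.081 at 0.50, 0.010 at 0.95).

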To definitively develop dermal carotenoid intensity as a biomarker of infant fruit and vegetable intake, we ultimately must conduct controlled feeding studies. In controlled studies, the dietary carotenoid inputs and dermal carotenoid responses will be carefully quantitated and can be correlated to develop predictive models relating the two, along with relevant covariates. However, before proposing controlled feeding studies in infants, we must address the following questions specific to this pediatric population: 1) Is skin carotenoid measurement feasible in infants at the finger and heel? 2) How do replicate measurements effect measurement reliability? 3) What are the mean skin carotenoid scores observed across infancy? 4) What are the mean carotenoid intakes and plasma carotenoid concentrations observed in infancy. 5) Are plasma carotenoid concentrations and carotenoid intakes associated with skin carotenoid scores in infants? Primary analyses will focus on 4 month olds.

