#### Inclusion Criteria:

Inclusion: infant is 4-4.5 months old at baseline; was born at term (>/=37 weeks gestation); is within the 5th-95th weight-for-age percentile (inclusive); primary caregiver can speak, read, and understand English; infants are exclusively breast- and/or formula-feeding at baseline. Exceptions to exclusive breast and formula feeding can be made if the infant has been fed a single-grain infant cereal, as is customary in some ethnic populations in Houston, or has consumed equal to or less than 1 teaspoon of solid food per week. Consenting parent or caregiver must be 18 years old or older.

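### Reliability is summarised only by an ICC, which mixes measurement error with between-infant spread; the within-infant error in score units should be reported beside it

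*Combined protocol and SAP*

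**What the plan says.** Reliability is half of Aim 1 in Section D: "To determine the feasibility and reliability of skin carotenoid measurement in infants". It is also one of the reasons given in G1 for the sample size of 21: "to estimate the reliability of skin carotenoid score measurements in 4 month olds". Section C sets the primary age: "Primary analyses will focus on 4 month olds".

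G2, Experimental Question 2, asks about "The effect of replicate measurements (3 versus up to 6 replicates) on measurement reliability in 4, 6, and 8 month olds". The approach is "Calculate the intraclass correlation coefficients and 95% confidence intervals using generalized linear mixed models with restricted maximum likelihood". The model is described as "Models specify a random replicate effect with nesting of replicates within infant and no covariates", and the index as follows: "ICC is calculated by dividing the variance effect for replicate by the total variance".

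No within-infant SD, standard error of measurement, coefficient of variation, repeatability coefficient or limits of agreement is planned. Experimental Question 3 adds a mean and SD of skin scores by age, but does not present that SD as a measure of repeatability.

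On diet, the Inclusion Criteria require that "infants are exclusively breast- and/or formula-feeding at baseline", with exceptions for single-grain cereal or a teaspoon or less of solids a week. The Exclusion Criteria bar isolated carotenoid supplements. No diet restriction is stated for the 6- and 8-month visits.

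**The concern.** An ICC is a ratio of variances. It can change because the device measures more or less precisely, or because the infants in the sample differ more or less from one another. The plan will produce ICCs at three ages, and the rules on diet differ between the first age and the other two. The skin score is meant to follow carotenoid intake, so its spread between infants may differ by age. Someone reading the three ICCs side by side could not tell which cause was at work.

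Two further things are at stake. Section C and Section I say the study prepares for controlled feeding studies, and planning those calls for the error in score units, which an ICC alone does not give. Experimental Question 2 also asks what extra readings achieve. An ICC for a single reading has the same expected value whether it is estimated from 3 or 6 readings, apart from small-sample effects; only its confidence interval narrows. It does not express the gain from averaging more readings.

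**Working it through.** **The plan's own figure.** G1 states that 21 infants suffice. It gives no target ICC, interval width, between-infant SD or within-infant SD, so there is nothing to reproduce. The SDs below are assumptions chosen to show how the index behaves.

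**Formulas.** One-way random-effects model with between-infant SD *B*, within-infant SD *W* and *k* readings:

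- conventional single-reading ICC = B² / (B² + W²)
- ICC for the mean of k readings = B² / (B² + W²/k)
- same-visit standard error of measurement for a mean of k = W / √k
- repeatability coefficient for two means of k = 1.96 × √2 × W / √k
- if the replicate term in G2 means within-infant variance, the index as written = W² / (B² + W²)

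**Spread varied, error held fixed.** Assume W = 20 units (W² = 400) throughout. For B = 15, for example, 225 / (225 + 400) = 0.36, and for the mean of three readings 225 / (225 + 133.3) = 0.63.

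| Assumed B | Single-reading ICC | ICC, mean of 3 | ICC, mean of 6 | Index if numerator is within-infant variance |
|---|---|---|---|---|
| 15 | 0.36 | 0.63 | 0.77 | 0.64 |
| 20 | 0.50 | 0.75 | 0.86 | 0.50 |
| 30 | 0.69 | 0.87 | 0.93 | 0.31 |
| 60 | 0.90 | 0.96 | 0.98 | 0.10 |

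The error is identical in every row:

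- 1 reading: standard error 20; repeatability 1.96 × 1.414 × 20 = 55.4 units
- 3 readings: standard error 20 / √3 = 11.5; repeatability 32.0 units
- 6 readings: standard error 20 / √6 = 8.2; repeatability 22.6 units

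The last column of the table shows why the numerator matters. If it is within-infant variance, a wider spread lowers the index, and any apparent trend with age reverses.

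**Simulation check.** With 21 infants, 3 readings, W = 1 and B = 0.5, 1 and 2 (4,000 runs each), the mean single-reading ICC was 0.20, 0.48 and 0.79. The mean estimated within-infant SD was 0.99 each time.

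**Precision at 21 infants.** The F-based 95% interval for an observed single-reading ICC of 0.50 is about 0.24 to 0.73 with 3 readings and 0.32 to 0.70 with 6. The within-infant SD has 21 × 2 = 42 degrees of freedom with 3 readings, so its 95% limits are 0.82 and 1.27 times the estimate (16.5 to 25.4 units if the estimate is 20). With 6 readings there are 21 × 5 = 105 degrees of freedom, and the factors are 0.88 and 1.16 (17.6 to 23.1 units). The study can therefore estimate the error in score units with useful precision.

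**The case against.** The strongest objections concern how far the point reaches, and several of them stand.

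- *Narrower spread at 4 months.* A reader might infer that the entry criteria do narrow the spread, so that the 4-month ICC will look poor and then improve. The documents do not show this. They give no SD of skin scores at any age. Breast-fed, formula-fed and mixed-fed infants are all eligible, and Section N treats milk as a source of carotenoids, so spread at 4 months could be wide. The unclear numerator leaves the direction open as well.
- *All comparisons distorted by diet.* Experimental Question 2 states only one comparison, 3 against up to 6 readings. Made in the same infants at one age, it has the same diets on both sides. So does finger against heel at one visit, which Question 2 does not mention. Only reading ICCs across ages is exposed to differing diets.
- *The device might be wrongly rejected.* No ICC threshold or go/no-go rule is given, and Section I calls the data preliminary.
- *The ICC has its own use.* Aim 3 concerns correlation with plasma carotenoids and intake, and there the ability to tell infants apart is the relevant property. That is a reason to keep the ICC prominent.
- *Error may not be constant.* F2 expects some fingers to be too small for a reproducible reading, so error itself may change with age, or with score level. This supports measuring error directly.
- *Question 3 already gives an SD by age.* One could compute SD × √(1 − ICC), but only if that SD is for single readings and the ICC is conventional. The plan states neither, and this route gives no confidence interval directly.

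Replicates taken at one visit also leave out between-visit error. The added measure would therefore be only part of what a feeding study needs.

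**Conclusion.** The point holds in a limited form. The ICC is the only planned reliability measure. It cannot separate measurement error from between-infant spread when read across 4, 6 and 8 months, and in its single-reading form it does not show the benefit of more readings. The size in this trial is unknown. The range of 0.36 to 0.90 rests on an assumed within-infant SD of 20 and assumed between-infant SDs of 15 to 60, and shows only what is possible. The documents do not establish that spread is narrower at 4 months, that the ICC will rise with age, or that any decision about the device would turn on it. Nothing planned is invalid: this is a free improvement that adds to the ICC and does not replace it.

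**What to change.** Amend G2, Experimental Question 2, as follows.

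1. State that the ICC numerator is the between-infant variance, and whether the ICC refers to a single reading or a mean.
2. From the same mixed model, report for each age and each site (finger, heel) the between-infant SD, the within-infant SD in score units with its 95% CI, and the resulting same-visit standard error of measurement or repeatability coefficient for 1, 3 and 6 readings. Show these alongside the ICC.
3. Check whether within-infant error rises with the score level. If it does, report it on a log or CV scale.
4. Use the within-infant SD (or its log or CV equivalent) when comparing measurement error across ages or sites.
5. State that same-visit replicates do not include between-visit error.

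The cost is wording and a few extra table columns. The variance components come from the model already planned, and no new data or visits are needed.

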#### F2. Procedure

Overall Study Design: Caregivers will be phone pre-screened to review subject eligibility. Pre-screened subjects and the primary caregiver will be invited to the Children's Nutrition Research Center (CNRC) Metabolic Research Unit (MRU) for on-site screening, consent, and baseline 4-month-old assessments between 4 and 4.5 months of age. Subjects and their primary caregiver will return between 6-6.5 and again between 8-8.5 months of age. At each visit,

caregivers will complete a 7 day food frequency questionnaire (FFQ) on behalf of the infant, an optional infant blood sample will be drawn, infant dermal carotenoid intensity, length, weight, and body fatness will be measured. One week prior to the 6- and 8-month-old visits, the primary caregiver will complete an online secure food intake questionnaire for 3 separate days to provide a 24-hour dietary recall for the infant. A research staff member may contact the caregiver the next day about any questions regarding the 24 hour dietary recall. Lactating mothers will be asked to provide an optional breast milk sample at study visits if they are currently breastfeeding.

Contact 1: Recruitment (less than 1 hour): Subjects will be recruited in-person, by posted flyers, or be social media advertising. For details on recruitment locations, see the attachment "H-43692 Recruitment Sites".

Contact 2: Pre-screening phone/secure video call or in-person interview (less than 1 hour): Review of eligibility and invitation for consent and enrollment will be accomplished by e-mail, phone call, or with the participant's permission, in-person at the point of recruitment. The interested adult will be pre-screened to assess general availability and eligibility for the study. If deemed potentially eligible, they will be invited to the CNRC or secure video call for Contact 3a. If too young, we will waitlist and phone/text/email to confirm eligibility/interest.

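### G1 rests n=21 partly on a 4-month skin-carotenoid association, but G2's only model for it gives one slope per predictor, shared across 4, 6 and 8 months and both skin sites, with no check that the slopes are equal

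*Combined protocol and SAP*

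**What the plan says.** Section G1 sets enrolment at "Local: 21 Worldwide: 21" and names four things this number is enough for, all in 4 month olds: the mean measurement time, the reliability of the skin score, its mean and SD, and, fourth, to "examine the correlation between skin carotenoid scores and plasma carotenoid concentrations and carotenoid intake in 4 month olds". Section C gives the same emphasis: "Primary analyses will focus on 4 month olds".

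Section G2 takes up the fourth purpose only under its Exploratory Questions. There the question covers the skin score at finger or heel "with dietary carotenoid intake and total plasma carotenoid concentrations in 4, 6, and 8 month olds". The one stated approach is "Generalized linear mixed models controlled for age, skin measurement location, and their interaction, with either plasma carotenoids or dietary carotenoid intake as predictors" of the skin score. G2 mentions a 4-month priority once, for measurement time in Experimental Question 1.

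Two design facts bear on this. At entry, "infants are exclusively breast- and/or formula-feeding at baseline", with narrow exceptions for single-grain cereal or a very small amount of solid food. And at each visit "an optional infant blood sample will be drawn".

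**The concern.** Age, location and their product let the mean skin score differ across the six age-by-site cells. They do not let the relation between skin score and carotenoids differ across those cells. An analyst who follows G2 exactly obtains one plasma slope and one intake slope, and no association specific to 4 months, to the finger or to the heel.

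At stake is one of the four purposes offered for the sample size, and the part of Aim 3 that belongs to the age of primary interest. If slopes are the same everywhere, the pooled slope is right and more precise. If they are not, it is an average whose weights depend on how much the predictor varies at each visit, and nothing in the planned output would reveal this. The feeding criterion at entry is a reason not to take equality for granted: the source of carotenoids can change as complementary foods come in.

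**Working it through.** **1. The plan's own figure.** G1 gives no target correlation, power, alpha or interval width, so n=21 cannot be reproduced. The check is therefore of what the stated model estimates.

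**2. The model as written.** For infant i, age a, site l and predictor x (plasma or intake):

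skin score = age effect + site effect + (age × site) effect + β·x + random effects.

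There is one β per predictor. No x × age or x × site term is named. G2's Question 3 gives 4-month means and SDs, which are not associations.

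**3. What β estimates if slopes differ.** Let b4 be the 4-month slope, b4 + d the slope at both later ages, and w the share of the pooled slope contributed by the 4-month data. Then

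pooled slope = w·b4 + (1 − w)(b4 + d) = b4 + (1 − w)d.

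The miss is (1 − w)d, and it is zero when d = 0.

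**4. Size of w.** The documents give no slopes, spreads or variances, so these inputs are assumptions: 21 infants with complete data at 3 ages and 2 sites; variance components of 0.25 (infant), 0.25 (visit) and 0.36 (residual); 4-month predictor SD of 1; later SD equal to k; correlation of the predictor between visits from 0 to 0.7. The weights are generalized least squares weights after removing the six cell means, averaged over 1,500 runs per setting.

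| k (later SD / 4-month SD) | w | miss, (1 − w)d |
|---|---|---|
| 0.67 | 52-60% | 0.40d to 0.48d |
| 1 | 33% | 0.67d |
| 1.5 | 13-18% | 0.82d to 0.87d |
| 2 | about 5-11% | 0.89d to 0.95d |

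Hand check at zero correlation between visits: w ≈ 1/(1 + 2k²), which gives 1/1.90 = 53%, 1/3 = 33%, 1/5.5 = 18% and 1/9 = 11%.

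**5. Direct simulation** (assumed slopes, 200 runs, random infant intercept, equal spread at each age). With true slopes 0, 0.4 and 0.8 at 4, 6 and 8 months, the G2 model gives a mean slope of 0.41; adding x × age recovers 0.01 at 4 months. With all slopes 0.5, the two models give 0.49 and 0.48, with empirical SDs of 0.09 (pooled) and 0.17 (4-month slope).

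**6. Precision of a 4-month correlation.** 95% CI = tanh(atanh(r) ± 1.96/√(n − 3)). At an assumed r = 0.5, atanh(r) = 0.549.

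- n = 21: 0.549 ± 0.462, giving 0.09 to 0.77
- n = 18: 0.549 ± 0.506, giving 0.04 to 0.78
- n = 15: 0.549 ± 0.566, giving −0.02 to 0.81
- n = 12: 0.549 ± 0.653, giving −0.10 to 0.83

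Total enrolment is 21 and infant blood is optional, so the plasma row that applies may be one of the lower ones.

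**The case against.** The strongest reply is that G2 calls this analysis exploratory, that Aim 3 speaks of infants in general, and that G1 promises only to look at the correlation, with no claim of power or precision. On that view the pooled slope is a legitimate answer and G1 could simply be reworded to describe a pooled association. Much of this stands: it limits the point to an improvement. But rewording G1 alone would leave Section C's focus on 4 month olds, and G2's own mention of finger or heel, without an estimate.

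The phrase about the interaction might also be read loosely to include the predictor. The grammar points to age by location; if more was meant, the plan needs to say so.

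Three stronger readings are tempting and should not be drawn.

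- A reader might infer that the pooled slope mostly reflects the later visits. The documents give no spread of plasma carotenoids or intake at any age. Milk is itself a carotenoid source under study, and breast-fed, formula-fed and mixed-fed infants are all eligible, so the 4-month spread could be the larger one. The illustration runs in both directions.
- A reader might infer from the Dietary Assessment text that fruit and vegetable intake is assessed only later. It is not: the food frequency questionnaire covers these foods at every visit, and Contacts 4 to 7 place recalls in the week after the 4-month visit. Only the feeding criterion at entry supports a difference in diet.
- A reader might infer that n=21 is wrong. That is not shown; it cannot be checked without design inputs.

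**Conclusion.** The point holds on the text alone: G1 cites a 4-month association, and no analysis stated in G2 delivers it, by age or by site, unless slopes are equal. The size of any error is unknown. It is zero with equal slopes; on the assumptions above, including equal follow-up, it ranges from 0.40 to 0.95 of the slope difference, depending on relative spread that the documents do not report. The random-effects structure used in the illustration is also assumed, since G2 states none for this model.

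The reduced plasma n is a secondary point about precision and adds no weight to the first. G1's other three purposes each have an analysis in G2 that covers 4 month olds and are unaffected. This is a cheap improvement to an exploratory analysis and not a flaw that invalidates the plan.

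**What to change.** 1. In G2, keep the pooled model and add: *This model assumes that the slope for each predictor is the same at all ages and at both skin sites.*
2. Add the check: *An exploratory model will add predictor-by-age and predictor-by-location terms; these interactions will be reported with 95% CIs.* With 21 infants, an interval that includes zero will not establish equal slopes, so the intervals should be reported as they are and not used to choose a model.
3. Add the estimate: *In 4 month olds, the correlation (Fisher-z 95% CI) and linear-regression slope (95% CI) of the infant's mean skin score on each predictor will be reported separately for finger and heel. These analyses are exploratory and not adjusted for multiplicity.* Two predictors by two sites makes four analyses.
4. Name the intake instrument, the same one for the pooled and 4-month analyses. G2 does not say whether intake comes from the questionnaire or the recalls, and around the 4-month visit these cover different weeks.
5. In G1, say that plasma analyses use only infants who give the optional blood sample, so n may be below 21, and show the expected interval over a range such as 12 to 21.

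The cost is wording and a few models on data already being collected. The downside is width: on the same assumed variance components, with slope 0.5, equal predictor SDs and t intervals, the 95% half-width at n=21 is 0.20 to 0.25 for the pooled slope and about 0.445 for a 4-month slope at one site. At n=15 these become 0.24 to 0.31 and about 0.555.
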